### 5.10.2.2 Sites Performing Correlative Study

WES and RNAseq will be performed by the MoCha Laboratory, and Infinium Methylation assays will be performed by the laboratory of [name] at the Translational Genomics Research Institute (TGen).

Genomic profiling will be performed systematically on a separate sample of the bone marrow aspirate, or a “second pull” obtained specifically for biomarker studies. WES study, RNAseq, and methylome will require relatively low amount of nucleic acids with 100 ng of DNA for WES or methylome and 100 ng of RNA for the RNAseq.

## 5.10.3 Pharmacometabolomic Profiling

### 5.10.3.1 Specimen(s) Receipt and Processing at the Karmanos Cancer Institute Pharmacology Core

Samples will be processed according to institutional SOPs.

### 5.10.3.3 Specimen Receipt and Processing

We will apply a LC-MS/MS based targeted metabolomics platform to define the plasma metabolic signature of olaparib exposure in AML patients. Metabolic profiling will be performed in the pre- and post- olaparib treatment plasma samples using a targeted metabolomics platform, which has been established in the KCI Pharmacology Core. This platform can quantitatively measure about 300 metabolites that are involved in major human metabolic pathways (Table 2). All LC-MS/MS analyses were performed on an

AB SCIEX QTRAP 6500 LC-MS/MS system. Analyst 1.6 software was used for system control and data acquisition and MultiQuant 3.0 software was used for data processing and quantitation.

**Table 2** Typical endogenous metabolites measured by the LC-MS/MS based targeted metabolomics platform.

Classes or Pathways	Number of Metabolites
Glycolytic, TCA cycle, and pentose phosphate pathway	25
Nucleosides, nucleotides and NAD-related metabolites	40
Amino acid and related metabolites	60
Acyl CoAs	10
Acyl Carnitines	20
Bile acids	15
Ceramides	10
Steroids	10
Short chain fatty acids	8
Phospholipids	15
Gut microbial related metabolites	15
Miscellaneous Metabolites	65
Total	293

#### 5.10.4 Creation of Patient-Derived Xenograft (PDX) Models from Baseline Bone Marrow Biopsies.

##### 5.10.4.1 Specimen Receipt and Processing at Yale University

Specimens will be processed according to institutional SOPs.

##### 5.10.4.2 Sites Performing Correlative Study

PDX modeling will be performed in the laboratories of [name] and [name] at Yale University.

We will stratify MDS/AML PDX mice to treatment arms via pre-treatment determination of engraftment levels in peripheral blood and bone marrow via aspiration. We will determine 2HG levels in plasma before and after treatment. At conclusion of the treatment we will euthanize animals and determine treatment efficacy via comprehensive analysis that includes complete blood count (CBC), flow cytometric analysis for human cell percentage and differentiation, histology, hematopoietic and non-hematopoietic organ infiltration, and spleen size. In addition, to determine the efficiency of the treatment to eliminate the leukemia stem cell we will perform single cell RNAseq and serial transplantation into tertiary recipients to phenotypically and functionally assess possible persistence of leukemic stem cells.

#### 5.10.5 Evaluation of the clonal heterogeneity evolution by single cell DNA sequencing

##### 5.10.5.1 Specimens will be processed according to institutional SOPs

### 5.10.5.2 Sites performing correlative study

Single cell DNA sequencing will be performed in the laboratories of [name] and [name] at Yale University

We will use patient’s bone marrow samples collected at enrollment and after Cycles 1 [optional], 3, 6, 12 and at end of treatment. Mononuclear cells will be separated using a Ficoll Hypaque purification method and viably cryopreserved in FBS 90%/DMSO10% or other appropriate freezing medium. At time of sequencing batches of 4 samples will be processed at the same time and evaluated using the Mission Bio Tapestri single cell DNA sequencing platform. A minimum of 10^4 living cells are required to proceed for each sample and we will be using the commercially available 45-gene panel. We will compare the evolution of the subclones at the different stages of the treatment, evaluate the proportion of IDH mutated clones persisting after treatment, evaluate the co-mutations as well as the most common mechanisms of resistance (e.g. IDH mutation switch, development of a RAS or FLT3 mutant clone). A subset of the samples (e.g. patients with concomitant IDH and SRSF2 mutations) will be evaluated with a customized panel and another subset of patients will be evaluated using a multi-omic approach using in parallel a barcoded cytometry antibody panel.

## 6. TREATMENT PLAN

### 6.1 Agent Administration

Treatment will be administered on an outpatient basis. Reported AEs and potential risks are described in Section 10. Appropriate dose modifications are described in Section 7. No investigational or commercial agents or therapies other than those described below may be administered with the intent to treat the patient's malignancy.

Regimen Description					
Agent	Premedications / Precautions	Dose	Route	Schedule	Cycle Length
Olaparib	
 
Do not consume grapefruit juice.
 
Olaparib tablets can be taken with or without food.
 
	If CrCl = 30 - 50 mL/min: 200 mg (2 x 100 mg tablets)	Tablet PO q12h	Daily	28 days (4 weeks)
		If CrCl > 50 mL/min: 300 mg (2 x 150 mg tablets)			

PO = oral administration, q12h = every 12 hours

- For patients with CrCl between 30 and 50 mL/min, the starting dose will be 200 mg bid.
- For patients with CrCl > 50 mL/min, the starting dose will be 300 mg bid.

NCI Protocol #: 10264

Version Date: December 11, 2024

#### 6.1.1 Olaparib

Patients will be administered olaparib every 12 hours (q12h). Olaparib tablets should be taken at the same time each day, approximately 12 hours apart with one glass of water. The olaparib tablets should be swallowed whole and not chewed, crushed, dissolved, or divided. Olaparib tablets can be taken with or without food. It is prohibited to consume grapefruit, grapefruit juice, or Seville oranges while on olaparib therapy.

If vomiting occurs shortly after the olaparib tablets are swallowed, the dose should only be replaced if all of the intact tablets can be seen and counted. Should any patient enrolled on the study miss a scheduled dose for whatever reason (*e.g.*, as a result of forgetting to take the tablets or vomiting), the patient will be allowed to take the scheduled dose up to a maximum of 2 hours after that scheduled dose time. If greater than 2 hours after the scheduled dose time, the missed dose is not to be taken and the patient should take their allotted dose at the next scheduled time.

The patient will be requested to maintain a medication diary (see Appendix F) of each dose of medication. The medication diary will be returned to clinic staff at the end of each course.

#### 6.1.2 Overdose

There is currently no specific treatment in the event of overdose with olaparib and possible symptoms of overdose are not established.

Olaparib must only be used in accordance with the dosing recommendations in this protocol. Any dose or frequency of dosing that exceeds the dosing regimen specified in this protocol should be reported as an overdose. Per the Olaparib Investigator's Brochure (2019), the Maximum Tolerated Dose is 300 mg twice daily (tablet).

Adverse reactions associated with overdose should be treated symptomatically and should be managed appropriately.

## **6.2 General Concomitant Medication and Supportive Care Guidelines**

Because there is a potential for interaction of olaparib with other concomitantly administered drugs, the case report form must capture the concurrent use of all other drugs, over-the-counter medications, vitamins, nutritional supplements, or alternative therapies at the time of enrollment and throughout the study. The case report form should capture the dates of administration (including start/end dates if known), dosage (including dosing frequency/schedule), and reason for use. The PI should be alerted if the patient is taking any agent known to affect or with the potential for drug interactions. The study team should check a frequently-updated medical reference for a list of drugs to avoid or minimize use of. Appendix B (Patient Drug Information Handout and Wallet Card) should be provided to patients if available.

### **6.2.1 Anti-Emetics/Anti-Diarrheal**

From screening part 2 onwards, should a patient develop nausea, vomiting and /or diarrhea, then these symptoms should be reported as AEs and appropriate treatment of the event given. An information sheet for patients regarding management and reporting of diarrhea can be found in Appendix E.

### 6.2.2 Medications that may NOT be administered:

#### Prohibited medications

Prohibited medication/class of drug:	
Anticancer therapy: Chemotherapy Immunotherapy Hormonal therapy* Radiotherapy (except palliative) Biological therapy including growth factors Other novel agents	Not permitted while the patient is receiving study medication.  Hydroxyurea up to 6 g/day in the context of the management of proliferative AML is allowed during screening and until the end of cycle 1. It should be discontinued as soon as possible based on investigator clinical judgement. Note the risk or severity of adverse effects can be increased when hydroxyurea is combined with olaparib.  Intrathecal chemotherapy for maintenance (but not active treatment of CNS disease) of a controlled CNS disease is allowed.
Live virus vaccines Live bacterial vaccines	Not permitted while the patient is receiving study medication and during the 30 day follow up period. An increased risk of infection by the administration of live virus and bacterial vaccines has been observed with conventional chemotherapy drugs and the effects with olaparib are unknown.

\*Hormone Replacement Therapy (HRT) is acceptable

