### 2.4.2 Integrated Biomarkers

#### 2.4.2.1 Peripheral blood and bone marrow 2HG levels

The main objectives of this assay are to: 1) correlate the chances of response to olaparib with baseline 2HG levels and 2) evaluate the longitudinal variations of 2HG levels as a marker of response to treatment and progression.

Based on our experience, as detailed in the background section, the “BRCAness” of IDH mutated patients is related to the exposure of the cell to 2HG. We hypothesize that patients with elevated levels of 2HG may have a better response to olaparib. We also want to confirm that olaparib is able to reduce the levels 2HG and maintain low levels of 2HG in treated patients.

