### **3.2 Exclusion Criteria**

3.2.1 Patients with acute promyelocytic leukemia.

3.2.2 Patients with active central nervous system (CNS) leukemia or requiring maintenance intrathecal chemotherapy.

3.2.3 Patients receiving concurrent chemotherapy, radiation therapy, or immunotherapy for AML/MDS.

3.2.4 Patients actively receiving any other investigational agents.

3.2.5 Management of treatment for patients with co-occurring mutations, like FLT3, will be prioritized by the treating physician after discussion of treatment options with the patient

3.2.6 Hyperleukocytosis with >50,000 WBC/mcl. Hydroxyurea for WBC count control is permitted before starting treatment and may be continued until Day 28 of Cycle 1. The

maximum dose of hydrea will be 6 grams per day. Patients will be withdrawn from the study if  $>50,000$  WBC/mcl occur or recur  $>14$  days after starting treatment on the study.

- 3.2.7 Active, uncontrolled infection. Patients with infection controlled with antibiotics are eligible.
- 3.2.8 Patients considered a poor medical risk due to a serious, uncontrolled medical disorder, non-malignant systemic disease or active, uncontrolled infection. Examples include, but are not limited to, uncontrolled ventricular arrhythmia, recent (within 3 months) myocardial infarction, uncontrolled major seizure disorder, unstable spinal cord compression, superior vena cava syndrome, extensive interstitial bilateral lung disease on High Resolution Computed Tomography (HRCT) scan or any psychiatric disorder that prohibits obtaining informed consent.
- 3.2.9 Patients who are pregnant or nursing. Pregnant women are excluded from this study because olaparib is a PARP inhibitor with the potential for teratogenic or abortifacient effects. Because there is an unknown but potential risk for AEs in nursing infants secondary to treatment of the mother with olaparib, breastfeeding should be discontinued if the mother is treated with olaparib. These potential risks may also apply to other agents used in this study.
- 3.2.10 Resting electrocardiogram indicating uncontrolled, potentially reversible cardiac conditions, as judged by the investigator (*e.g.*, unstable ischemia, uncontrolled symptomatic arrhythmia, congestive heart failure, QTcF prolongation  $>500$  ms, electrolyte disturbances, *etc.*), or patients with congenital long QT syndrome.

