### 5.7 Biomarker Plan

#### List of Biomarker Assays in Order of Priority

Priority	Biomarker Name	Biomarker Assay	Biomarker Type and Purpose	M/O	Specimen(s) and Time Point(s)	Laboratory Performing Assay
1	IDH1/2 Mutation	DNA sequencing or PCR	
 
Integral
 
Eligibility criteria
 
	M	
 
Bone marrow aspirate
 
Enrollment
 
	Local CLIA-certified laboratory
2	2HG Levels	LC-MS/MS	
 
Integrated
 
Potential biomarker of response
 
	M	
 
Plasma
 
Enrollment, after Cycles 1, 3, 6, 9, 12, and end of treatment
 
	[name], Karmanos Cancer Institute [contact]
3	2HG Levels	LC-MS/MS	
 
Exploratory
 
Potential biomarker of response
 
	M/O	
 
Bone marrow aspirate
 
Mandatory: enrollment
 
Optional: after Cycles 1, 3, 6, 9, 12, and end of treatment
 
	[name], Karmanos Cancer Institute [contact]
4	Genomic Profiling	Whole exome sequencing	
 
Exploratory
 
To evaluate clonal evolution and clonal architecture
 
	M/O	
 
DNA from buccal swab (enrollment only)
 
DNA from bone marrow aspirate*
 
DNA from blood
 
Mandatory: enrollment, after Cycles 1, 3, 6, 9, and 12
 
Optional: end of treatment
 
End of Cycle 1: IDHi-naïve cohorts only
 
	[name] – MoCha, National Cancer Institute [contact]
5	Genomic Profiling	RNA sequencing	
 
Exploratory
 
To evaluate clonal evolution and clonal architecture
 
	M/O	
(Will be assessed using RNA from bone marrow aspirate and blood obtained from WES biomarker.)
 
 
Mandatory: enrollment, after Cycles 1, 3, 6, 9, and 12
 
Optional: end of treatment
 
End of Cycle 1: IDHi-naïve cohorts only
 
	[name] – MoCha, National Cancer Institute [contact]

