#### 9.5.1 Changes in 2HG Levels

The Mann-Whitney U test will be used to test for differences in post-treatment plasma 2HG concentrations between patients with a response to treatment and those without. We will also test for differences in  $\Delta$ 2HG (defined as pre-treatment minus post-treatment plasma concentration) between patients with a response to treatment and those without. Differences with  $p \leq 0.05$  will be considered significant. The area under the receiver operating characteristic curve (ROC AUC) will be calculated to determine the cutoff value of the  $\Delta$ 2HG difference. The optimal cutoff value will be determined at the point on the ROC curve at (sensitivity + specificity - 1) is maximized (Youden index).

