- e: Response Assessment includes bones marrow biopsy, and marrow and plasma 2HG levels. Response per AML IWG (IWG) 2003 criteria and MDS IWG 2006 (modification) criteria.

- f: Clinical Safety Laboratory Assessments to occur twice weekly during Week 1 of Cycle 1, once weekly during Weeks 2-4 of Cycle 1, and then once per cycle. Assessment to include: Haematology/Haemostasis (whole blood), B-Haemoglobin (Hb), B-Leukocyte count, B-Absolute neutrophil count, B-Absolute lymphocyte count, B-Platelet count, B-Mean cell volume (MCV), Urinalysis (dipstick), U-Hb/Erythrocytes/Blood, U-Protein, U-Glucose, and Clinical Chemistry (serum or plasma): S/P-Creatinine, S/P-Bilirubin, total, S/P- Alkaline phosphatase (ALP), S/P-Aspartate transaminase (AST), S/P-Alanine transaminase (ALT), S/P-Albumin, S/P-Potassium, S/P-Calcium, total, S/P-Sodium, S/P-Urea or Blood Urea Nitrogen (BUN), S/P-Total Protein, S/P lactate dehydrogenases (LDH), S/P uric acid, & phosphorus
- g Coagulation evaluation to occur twice weekly during Week 1 of Cycle 1, once weekly during Weeks 2-4 of Cycle 1, and then once per cycle thereafter. Assessment to include activated partial thromboplastin time (APTT), Prothrombin Time/international normalized ratio (PT/INR), and Fibrinogen as indicated in the calendar, or as clinically indicated (*i.e.*, upon suspicion of DIC). Each coagulation test result will be recorded in CRF. Coagulation evaluation to be conducted pre-study, Cycle 1 Day 1, Cycle 1 Day 15, and Day 1 of Cycles 2, 4, 6, 9, 12, every third cycle after cycle 12, and at End of Treatment.
- H Blood and bone marrow collections to occur after the cycle.
- Note: Each Cycle is 28 days.; Visit Windows: Cycle 1 – 3 (+/-1 day); Cycle 4 – 12+ (+/-3 days); EOT +/- 7 days; 90 f/u +/-14 days

EOT= end of treatment, q12h = every 12 hours, PO = by mouth, BUN=blood urea nitrogen; LDH=lactic dehydrogenase; SGOT[AST]=serum glutamic oxaloacetic transaminase [aspartate transaminase]; SGPT[ALT]=serum glutamic pyruvic transaminase [alanine transaminase]. CRF = Case Report Form.

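### Section 9.5.1 ignores hydroxyurea, which is allowed when the baseline and possibly the first post-baseline 2HG samples are drawn, so cytoreduction could be mistaken for, or distort, a 2HG effect (exploratory analysis, size unknown)

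*Combined protocol and SAP*

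**What the plan says.** **Hydroxyurea.** The prohibited-medication table in Section 6.2.2 makes an exception for hydroxyurea, up to 6 g/day, whose use in the "management of proliferative AML is allowed during screening and until the end of cycle 1". It adds: "It should be discontinued as soon as possible based on investigator clinical judgement". Exclusion criterion 3.2.6 gives the same window without limiting it to AML: "Hydroxyurea for WBC count control is permitted before starting treatment and may be continued until Day 28 of Cycle 1". The Study Calendar (Section 11) states "Note: Each Cycle is 28 days", so Day 28 is the last day of cycle 1. No interval free of hydroxyurea is required before a 2HG sample.

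**2HG sampling.** The Biomarker Plan (Section 5.7) lists plasma 2HG as a mandatory integrated biomarker, drawn at "Enrollment, after Cycles 1, 3, 6, 9, 12, and end of treatment". A calendar footnote places the on-treatment collections after the cycle.

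**2HG analysis.** Section 9.5.1 has two Mann-Whitney comparisons of responders with non-responders. One uses post-treatment plasma 2HG. The other uses delta 2HG, "defined as pre-treatment minus post-treatment plasma concentration", followed by an ROC curve and a Youden cutoff. It has no covariate, stratum, exclusion or sensitivity analysis for hydroxyurea, and it does not say which visit is post-treatment.

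**Aim and data.** Section 2.4.2.1 says "We also want to confirm that olaparib is able to reduce the levels 2HG". Section 6.2 says "the case report form must capture the concurrent use of all other drugs", with dates, dosage and reason for use.

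**The concern.** Section 2.1 explains that 2HG is made by mutant IDH enzymes, and criterion 3.2.6 allows hydroxyurea to control the white-cell count. Fewer mutant cells could mean less plasma 2HG without any action of olaparib.

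Two uses of the 2HG data are exposed to this:

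- **Within patients.** All four arms in Section 9.1.1 receive olaparib, so no untreated group shows what cytoreduction alone does. A fall in 2HG would be open to two explanations, even if hydroxyurea use were the same in responders and non-responders.
- **Between responders and non-responders.** Hydroxyurea goes to patients with proliferative disease, who may also respond less often. Criterion 3.2.6 withdraws patients whose count exceeds 50,000/mcl more than 14 days after starting treatment, so the disease feature that prompts hydroxyurea also leads to early failure. If use is uneven, a 2HG–response association could be created or hidden.

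At stake is the reading of the trial's only integrated biomarker, mainly in the two AML arms.

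**Working it through.** The plan gives no power or error figure for the 2HG analysis, so there is none to reproduce. The check sets the windows side by side, works out the direction of the bias, and then illustrates its size.

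**1. Overlap**

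| Plasma 2HG sample | Hydroxyurea window (screening to Day 28 of cycle 1) |
|---|---|
| Enrollment | Inside |
| After cycle 1 | At the boundary: on, or soon after, the last permitted day |
| After cycles 3, 6, 9, 12 | Outside |

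Delta at every visit subtracts from the baseline value, so exposure at baseline carries into every delta.

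**2. Direction**

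Delta = pre − post. Take a patient whose unexposed 2HG is constant at an index of 100, and assume that hydroxyurea halves it.

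- Started after baseline, present at the later sample: 100 − 50 = +50, an apparent fall.
- Present at baseline, then stopped: 50 − 100 = −50, an apparent rise.
- Present at both: 50 − 50 = 0.

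**3. False-positive rate, illustration A**

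Assumptions, none from the documents: log 2HG at baseline has SD 1.0; within-patient SD is 0.5; 40% of patients respond; olaparib has no effect; 2HG is unrelated to response. Hydroxyurea multiplies the post value by 0.5 or 0.25. Tests are two-sided Mann-Whitney at 5%, with 4,000 simulated trials per setting (standard error near 5%: √(0.05 × 0.95 / 4,000) = 0.3 percentage points).

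| n | Use, responders / non-responders | 2HG cut | Post test | Delta test |
|---|---|---|---|---|
| 39 | 10% / 40% | 50% | 7.9% | 14.4% |
| 39 | 10% / 40% | 75% | 14.6% | 20.2% |
| 39 | 10% / 20% | 50% | 4.9% | 4.7% |
| 39 | 10% / 20% | 75% | 5.2% | 6.4% |

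A repeat of the 10% / 40% setting gave 13–18% for the delta test, hence about 13–20%. The same model gave about 4–9% for either group test with 10–14 patients. Thirty-nine is the full IDH-inhibitor-naïve AML arm and 14 the exposed AML arm (Section 9.1.1). Section 9.5 expects at least 10 samples per time point.

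The small-sample result is unsurprising. With 10 patients, the expected number exposed is 4 × 0.10 + 6 × 0.40 = 2.8. With 39 it is 15.6 × 0.10 + 23.4 × 0.40 = 10.9.

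**4. Masking and baseline exposure, illustration B**

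Assumptions: 17 responders and 22 non-responders; log-SD 1.0; pre/post correlation 0.7; use in 10% of responders and 50% of non-responders; 2HG cut by 25%, 50% or 75%.

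| Setting | Test | No hydroxyurea | 25% | 50% | 75% |
|---|---|---|---|---|---|
| No true link, use after baseline | Delta | 5% | 7% | 12% | 23% |
| No true link, use before baseline then stopped | Delta | 5% | 6% | 13% | 22% |
| True 70% fall in responders, use after baseline | Delta (power) | 85% | 71% | 51% | 28% |
| True 70% fall in responders, use after baseline | Post (power) | 94% | 89% | 75% | 35% |

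The second row shows that choosing a later visit does not protect delta if the baseline was drawn on hydroxyurea. With 5 versus 5 patients, false-positive rates stay at 3–7%, and delta-test power, 23% without hydroxyurea, falls to 17%, 12% and 7%.

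**5. Effect of stratifying**

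With hydroxyurea exposure as a stratum in illustration A, both group tests return to near or below 5%.

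**The case against.** The case for leaving the plan alone has real force.

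- **The tested visit is not stated.** A reader might infer that Section 9.5.1 uses every sample, including cycle 1. It does not say so. If the tested visit is cycle 3 or later, the post-treatment sample lies outside the permitted window and only the baseline effect on delta remains. This stands, and it is a reason to name the visit.
- **The second overlap is at the edge.** Hydroxyurea is to be stopped early, and the draw follows the cycle. How many patients would still be affected is unknown. This stands.
- **No measured effect.** A reader might infer that hydroxyurea is known to lower plasma 2HG. No section reports this. The mechanism is a reasonable inference; the effect size and the imbalance are assumptions.
- **The inflation depends on the inputs.** It largely disappears with 10–14 patients or with 10% versus 20% use, so 13–20% cannot be read as the plan's error rate.
- **A before/after error rate would be beside the point.** Section 9.5.1 has no paired test. Section 2.4.2.1 states an aim to show a reduction, so the concern there is attribution, not the error rate of a planned test.
- **Restricting the main analysis to unexposed patients has its own cost.** It would select by prognosis, and a flag for use on the day of the draw would miss recent use. This stands, and favours stratifying.
- **The stakes are low.** The tests are exploratory and no stopping rule uses 2HG. The dates are on the CRF, so the question could be examined at reporting, but choosing the method then would be post hoc.

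**Conclusion.** The point holds in a limited form. Hydroxyurea may be present at the baseline 2HG sample, and at or just before the end-of-cycle-1 sample if that is the post-treatment visit. Section 9.5.1 neither accounts for it nor names the visit. Attribution of a 2HG fall to olaparib is therefore open to question whatever the balance of use. The responder comparison is open to distortion only if use differs between the groups.

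The size is unknown. The simulated rates show that bias in either direction is possible; they do not estimate what will happen in this trial. They rest on an assumed 50–75% effect (25–75% in illustration B) and on markedly uneven use. A finding that the 2HG analysis is invalid, or that its false-positive rate is inflated as planned, would go beyond the documents. This is a minor, inexpensive improvement to an exploratory analysis.

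**What to change.** In Section 9.5.1:

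1. Name the post-treatment visit for the Mann-Whitney comparisons, delta 2HG and the ROC cutoff.
2. From the CRF dates, derive hydroxyurea exposure within a stated interval before each 2HG sample, not only use on the day of the draw. Record baseline and post-treatment exposure separately, because they move delta in opposite directions.
3. Keep the all-patient analysis, and add pre-specified post-treatment and delta comparisons stratified by that exposure, for example a stratified rank-sum test.
4. Show the ROC cutoff and any before/after 2HG summary also without the exposed samples.
5. State that a 2HG fall will not be attributed to olaparib unless it also holds in unexposed patients.

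The cost is SAP wording and a derived variable from data already collected. The downside is lower precision in the AML arms, where exposed patients may be few and strata sparse. No treatment rule, sampling time or primary analysis changes.
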